- 9) Patient has serum-creatinine >1.6 mg/dL and is considered to have severe renal insufficiency defined as calculated* creatinine clearance \leq 29 mL/min (National Kidney Foundation K/DOQI Guidelines). *Please note that if serum creatinine \leq 1.6 mg/dL, there is NO need for calculation of creatinine clearance.*

*Calculated creatinine clearance will be done using the Cockcroft-Gault method for

$$Cl_{cr} = \left[\frac{(140 - \text{age})(\text{wt}[\text{kg}])}{72 \cdot C_s} \right]$$

creatinine clearance: * 0.85 with $C_s =$ serum creatinine, and result reported in mL/min.

Note: Patients with moderate renal insufficiency (creatinine clearance 30-59 mL/min) according to NKF K/DOQI Guidelines may be included provided that serum PTH, serum 25-hydroxyvitamin D, serum calcium and serum phosphorus are all within normal limits.

Note: Patients with calculated creatinine clearance \leq 29 mL/min using the Cockcroft-Gault formula are ineligible *only* in those regions where this is required via documented regulatory request, subsequently approved by the SPONSOR.

- 10) Patient has received treatment with an agent that has an effect on bone including:
- a) estrogen with or without progestin within the prior 6 months (Note: vaginal estrogen creams used not more than 2 times per week are allowed)
 - b) raloxifene or other SERM (including tamoxifen), tibolone, or an aromatase inhibitor within the prior 6 months
 - c) sub-cutaneous calcitonin within the prior 6 months (Note: use of intranasal calcitonin either prior to or during the study is permitted)
 - d) any anabolic steroid use at any time
 - e) systemic glucocorticoids (\geq 5 mg/day of prednisone or equivalent) for more than 2 weeks in the prior 6 months
 - f) bisphosphonates: use of any oral bisphosphonate in the 6 months prior to screening; use of any oral bisphosphonate for more than 3 months within the prior 2 years, or lifetime use of more than 6 months total; any lifetime use of IV zoledronate (Note: one dose of IV pamidronate or I.V. ibandronate more than 1 year prior to screening is allowed.)
 - g) cyclosporin for more than 2 weeks within the prior 6 months
 - h) fluoride treatment at a dose greater than 1 mg/day for more than 2 weeks at any time

Product: MK-0822

13

Protocol/Amendment No.: 018-04

- i) strontium-containing products (more than 200 mg elemental strontium daily, including over-the-counter preparations such as OSTEONAL™) at any time
 - j) PTH (1-34 or 1-84) within prior 12 months

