 - k) current use of chemotherapy, or heparin
 - l) growth hormone at any time
 - m) cathepsin K inhibitor at any time
 - n) RANK ligand inhibitor at any time
 - o) activated Vitamin D (e.g., alphacalcidol) in the prior 3 months
 - p) current use of vitamin A (excluding beta carotene) >10,000 IU daily, unless willing to discontinue this dose during the study
 - q) vitamin D supplement > 1200 IU daily, and is unwilling to limit vitamin D supplement to ≤ 1200 IU daily (≤ 8400 IU weekly), with 5600 IU weekly provided as study medication, and up to 400 IU daily permissible as a component of multivitamin
 - r) protease inhibitors for HIV treatment at any time
 - s) Patient is taking anti-seizure medication, and indices of calcium metabolism are *not* within normal limits (Note: if indices of calcium metabolism [serum calcium, serum 25-hydroxyvitamin D and serum PTH] are within normal limits, the patient may enroll based on this criterion)
 - t) current use of systemically administered azole antifungals (for example, ketoconazole, fluconazole, itraconazole, miconazole, posaconazole, ravuconazole, and voriconazole).
- 11) Patient has a daily calcium intake of <1,200 mg and is unwilling to take study-prescribed supplements, such that her daily calcium intake is approximately 1200 mg.
- 12) Patient has a history or current evidence of any condition, therapy, lab abnormality or other circumstance that might confound the results of the study, or interfere with the patient's participation for the full duration of the study, such that it is not in the best interest of the patient to participate.
- 13) Patient has a history of malignancy ≤ 5 years prior to signing informed consent, except for adequately treated basal cell or squamous cell skin cancer or in situ cervical cancer. Patient has had, at any time, a history of melanoma, leukemia, lymphoma, or myeloproliferative disorder.
- 14) Patient is > 80 years old, AND has a history of recurrent falls (≥ 2 falls in 1 year).

Product: MK-0822

14

Protocol/Amendment No.: 018-04

- 15) Patient is currently participating in or has participated in a study with an investigational compound or device within 30 days prior to signing informed consent.
- 16) Patient is, at the time of signing informed consent, a user of recreational or illicit drugs or has had a recent history (within the last year) of drug or alcohol abuse or dependence.
- 17) Patient demonstrates hepatic dysfunction defined as:

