3.1.5 Rationale for Dose Regimen

Odanacatib phase I data gathered in healthy postmenopausal women demonstrate that 25 mg and 50 mg of odanacatib administered once weekly result in ~70% and ~60% suppressions of serum C-telopeptides and urine N-telopeptides, respectively, throughout the 7 day dosing interval. Studies were too short in duration (less than or equal to 6 weeks) for meaningful assessment of biomarkers of bone formation. Lower doses of odanacatib resulted in robust suppression of resorption biomarkers (~70%) early in the 7 day dosing interval, but also in sharply attenuated effects on resorption biomarkers

Product: MK-0822

9

Protocol/Amendment No.: 018-04

(~20%) in the latter half of the week. No safety signal was detected upon review of unblinded data from these Clinical Pharmacology studies. Based on the reassuring safety profiles associated with all tested doses, and the identical effects of 50 and 100 mg once weekly on biomarkers of bone remodeling in these studies, a top dose of 50 mg was selected for study in phase II trials.

Twenty-four month data from the ongoing phase IIb dose-ranging study conducted in 399 postmenopausal women with low bone mass (T-scores ≤ -2.0) revealed that odanacatib, at the top dose of 50 mg once weekly, resulted in 5.5% and 3.8% increases in lumbar spine and femoral neck BMD from baseline, respectively. By comparison, in historical trials, 24 months of alendronate treatment dosed at 70 mg OW yielded aBMD increases of 5.2% and 2.8%, respectively [18]. Treatment with odanacatib 50 mg once weekly for 36 months yielded continuing BMD increases at the lumbar spine and hip sites that were larger in magnitude than those historically seen with alendronate at these sites in a similar patient population [18].

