3.2 STUDY PROCEDURES

3.2.1 Concomitant Medication(s)/Treatment

Drugs specifically prohibited in the exclusion criteria are not allowed during the ongoing trial. Listed below are some specific restrictions for concomitant therapy use during the course of the study. If there is a clinical indication for one of these or other medications specifically prohibited during the study, discontinuation from blinded study therapy may be required. The investigator should discuss any questions regarding this with the local clinical monitor. The final decision on any supportive therapy rests with the investigator and/or the patient's primary physician. However, the decision to continue the patient on blinded study therapy requires the mutual agreement of the investigator, the SPONSOR, and the patients.

Bone-Active Agents

Except for the use of intra-nasal calcitonin, patients will not be entered into the study if, during screening, they express an intention to begin estrogen or any other anti-osteoporotic therapy before study completion. Drugs with an effect on bone are prohibited. Soy Isoflavones (e.g., Genistein, Daidzein, Isofem™) are considered estrogens.

If, following Randomization, a patient begins therapy with bisphosphonates, strontium, or PTH, the SPONSOR's Clinical Monitor must be contacted and blinded study therapy will likely be discontinued. In addition, patients who commence therapy with low-dose systemic estrogens for the management of menopausal symptoms *for 6 months or more* must discontinue blinded study therapy. These patients must continue to be followed in the study off-drug. Use of vaginal estrogen up to 2 times per week is permissible during the study.

Anti-fungals

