3.5 DATA ANALYSIS

This section outlines the statistical analysis strategy and procedures. A stand-alone Statistical Analysis Plan (SAP), which details the statistical issues and methods for the study was issued prior to the unblinding of the data for the first interim analysis. The current protocol amendment (018-02) incorporates all details from the stand-alone SAP, according to current Merck guidelines. A separate SAP was created for the PK/PD analyses. The protocol may be further amended if changes are made to the primary or important secondary analyses in the course of the study. Changes to other analyses will be listed in the Clinical Study Report for the study, along with an explanation as to why they occurred and when they occurred.

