3.5.4 Analysis Populations

For fracture endpoints a "Full-Analysis-Set" (FAS) population will be used. This will include all randomized patients, who took at least one dose of study medication, with follow-up from Randomization to study termination, without regard to protocol violations, compliance to study drug or early treatment discontinuation. Patients will be counted in the treatment group they were randomized to, irrespective of the treatment they actually received.

All available scans to determine morphometric vertebral fractures, will be used in the analyses. For morphometric fractures, a patient with no scan during the study will not be included in the FAS population. For the final analysis of clinical fractures, a calendar date (cut-off) will be determined when the pre-specified number of fracture events are seen. For the analysis of clinical fractures, patients who did not have a fracture by the time of the cut-off date will be censored at the cut-off date, unless they discontinued the study earlier, then they will be censored at the date of the last contact with the patient (either

Product: MK-0822

46

Protocol/Amendment No.: 018-04

telephone contact or study visit). Clinical fractures after the cut-off date will not be included in the analysis.

As a supportive approach, vertebral, non-vertebral and hip fracture analyses will also be performed based on the "Per-Protocol" (PP) population, to investigate the influence of missing data and protocol violators on the treatment effect. This approach excludes patients from the FAS population if they have important protocol deviations. Specific criteria to exclude a patient are identified in appendix 6.7, prior to unblinding of study database and will be based on a patient's compliance to study medication, the use of prohibited previous or concomitant medication, and the presence of secondary diagnoses which may influence the efficacy results. Data will be censored at the date of the last dose of study medication plus 30 days, for patients who did not have a clinical fracture by that time. The per-protocol analysis will not be performed if less than 10% patients (included in the FAS approach) are protocol violators.

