The per-protocol analysis set excludes patients and/or data points that represent clinically important deviations from the protocol-specified criteria, and so should not be considered a repetition of the inclusion and exclusion criteria defined in the protocol, but rather as a clinical assessment of protocol-specified deviations that may affect or confound the measures of efficacy. The per-protocol analysis will be performed as the primary approach for the biochemical marker data and may be performed as a secondary analysis for the primary endpoints (morphometric vertebral, hip and non-vertebral fractures). The per-protocol analyses for fractures will not be performed if less than 10% patients (included in the FAS approach) are protocol violators.

The listing of patients/data points who will not be included in the per-protocol analyses will be provided before frozen file.

The following rules will be applied to exclude patients/data points from the per-protocol analysis:

All Efficacy Analyses

1. Patient was <3 years postmenopause at baseline.
2. Missed >4 consecutive doses, or was <75% compliant with study medication before the biomarker measurement.

For fractures: Data will be excluded from the PP analysis from the time point onwards when >12 consecutive doses were missed, irrespective of the timing in the study. For time point more than 6 months (180 days) from start of prime therapy data will also be disregarded from the PP analysis when the total period off-drug (not necessarily consecutive doses) is more than 25% of the time in the study. Fractures

Product: MK-0822

32

Protocol/Amendment No.: 018-04

after this time point will be disregarded and the patient will be censored at the first time point where she is considered a protocol violator².

3. Patient had a history of primary parathyroid disease within 2 years prior to entry (not cured by parathyroidectomy), with elevated PTH or serum calcium greater than the upper limit of normal at baseline.
4. Patient has a history of secondary hyperparathyroidism.
5. Patient has a history of hypocalcemia (<8.5 mg/dL, corrected for albumin), accompanied by an elevated PTH at baseline (>65 pg/mL).
6. Patient has a baseline TSH <0.1 microIU/mL.
7. Patient has a history of a metabolic bone disorder, other than osteoporosis (examples include Paget's Disease of Bone, osteogenesis imperfecta, osteomalacia, renal osteodystrophy).

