8. Use of the following medications prior to randomization or concomitantly during the study (the doses and durations of specific treatments which will classify a patient as a protocol violator, based upon either prior or concomitant use, will be defined after data are available for review, but prior to unblinding for the first efficacy interim analysis). Patients/data points will be excluded from the start of the concomitant medication onwards.
 - anabolic steroids or glucocorticoids (≥ 5 mg/day prednisone or equivalent),
 - oral bisphosphonates (including alendronate, risedronate, clodronate, etidronate, ibandronate, or tiludronate),
 - I.V. bisphosphonates (including zoledronate, ibandronate, pamidronate),
 - cathepsin K inhibitor,
 - cyclosporine,
 - fluoride,
 - strontium,
 - PTH,
 - phenytoin, chemotherapy, heparin, or growth hormone,
 - estrogen \pm progestin (excluding topical applications), raloxifene, lasofoxifene, or other SERM, tamoxifen, tibolone, or an aromatase inhibitor,

² The number of missed consecutive doses was increased from 4 to 12 because the lower number was deemed overly stringent, as it equaled only 1 month of therapy, compared to approximately 3 months for 12 doses. In addition, it was felt that overall compliance with study medication was of greater importance after the first 6 months of treatment, as the effects of odanacatib on bone mineral density and bone strength (and hence fracture risk) have been shown to be time-dependent. Lower compliance during the first 6 months of the study is less likely to have a negative impact on the overall treatment effect, as fracture rates during this time period are more likely to be influenced by the patient's baseline level of risk, and yet to be altered by treatment.

Product: MK-0822

33

Protocol/Amendment No.: 018-04

- vitamin A (retinol and/or its esters); beta-carotene use is permitted,
- vitamin D (excluding study-provided concomitant vitamin D)

Biochemical Markers and Indices of Calcium and Mineral Homeostasis

Patients will not be included in the biochemical marker analyses for one or more of the reasons listed above. In addition, for the biochemical markers of bone resorption (u-NTx, s-CTx), a value will be excluded from the analysis if the last dose of study medication prior to the value is taken >7 days prior to the value, and for biochemical markers of bone formation (BSAP, P1NP) if the last dose of study medication is taken >30 days prior to the value.

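### The medication list that defines per-protocol violators (Appendix 6.7, item 8) leaves out RANK ligand inhibitors, a bone-active class the protocol prohibits

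*Protocol*

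**What the plan says.** Exclusion criterion 10 (Protocol Section 2.3) opens with "Patient has received treatment with an agent that has an effect on bone including" and lists 20 entries, (a) to (t). Entry (n) reads "RANK ligand inhibitor at any time". Section 3.2.1 does not allow drugs barred at entry to be used during the trial, and adds that "Drugs with an effect on bone are prohibited".

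Section 3.5.4 rests per-protocol exclusion on three things, one of which is "the use of prohibited previous or concomitant medication", and refers the reader to Appendix 6.7 for the specific criteria. There, under Description of Protocol Violations, the rules are introduced by "The following rules will be applied to exclude patients/data points from the per-protocol analysis". Item 8 covers "Use of the following medications prior to randomization or concomitantly during the study" and names the drugs. It defers the qualifying doses and durations to a later blinded decision and removes data from the start of the concomitant drug onward.

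The per-protocol set is the primary approach for the biochemical markers, which are measured in a 10% subset. For the three primary fracture endpoints it is supportive, and it is not run if fewer than 10% of FAS patients are violators.

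**The concern.** A drug class that the protocol itself counts as acting on bone, and prohibits both before and during the study, does not make anyone a per-protocol violator. Item 8 has no catch-all for other bone-active agents, and what it defers does not reopen the choice of drugs. A later SAP cannot be assumed to fill the gap, because Section 3.5 says the protocol "incorporates all details from the stand-alone SAP".

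The per-protocol set would then keep values it exists to remove. If use falls mainly on placebo, where women have most reason to seek other treatment, the treatment difference is diluted. This bears most on the resorption markers, which carry a formal secondary hypothesis and their own Hochberg family.

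**Working it through.** The protocol states no figure on this point to reproduce. The check is a comparison of lists, followed by an illustrative sizing.

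**1. Criterion 10 against item 8**

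| Entries in criterion 10 | In item 8? |
|---|---|
| (a), (b), (d)–(m), (o)–(q): 15 entries | Yes |
| (s) anti-seizure drugs | Partly (phenytoin only) |
| (c) subcutaneous calcitonin | No |
| (n) RANK ligand inhibitors | No |
| (r) HIV protease inhibitors | No |
| (t) systemic azole antifungals | No |

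Total: 15 + 1 + 4 = 20. The entries on either side of (n), cathepsin K inhibitors (m) and activated vitamin D (o), are both covered, as are growth hormone, heparin, fluoride and vitamin A.

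**2. Does another per-protocol rule catch the case?**

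- Items 1 and 3–7 concern menopausal status, diagnoses and baseline laboratory values. None refers to this class.
- Item 2 (missed doses, compliance), the marker limits of 7 and 30 days since the last dose, and fracture censoring at last dose plus 30 days all require that study tablets be stopped or missed.
- The rule on stopping blinded therapy in Section 3.2.3.9.1 names bisphosphonates, strontium and PTH. For other prohibited drugs, Section 3.2.1 makes discontinuation possible, not mandatory.

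Two cases remain: a woman who starts the drug and keeps taking her tablets, and a woman randomized in error after earlier use.

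**3. Size for the resorption markers**

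Assumptions: a fraction q = 0.005 to 0.02 of analysed placebo values is affected and none on odanacatib. The protocol gives no effect for RANK ligand inhibitors, so odanacatib's own suppression s stands in. Section 3.1.5 gives "70% and ~60% suppressions of serum C-telopeptides and urine N-telopeptides, respectively", so s = 0.7 and 0.6.

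The markers are analysed on the log scale, so the placebo geometric mean is multiplied by `(1 − s)^q`, and a true ratio of `1 − s` reads as `(1 − s) / (1 − s)^q`.

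| s | q | Placebo factor | True ratio | Ratio read |
|---|---|---|---|---|
| 0.6 | 0.005 | 0.9954 | 0.40 | 0.4018 |
| 0.6 | 0.02 | 0.9818 | 0.40 | 0.4074 |
| 0.7 | 0.005 | 0.9940 | 0.30 | 0.3018 |
| 0.7 | 0.02 | 0.9762 | 0.30 | 0.3073 |

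The placebo geometric mean falls by 0.5% to 2.4%. This does not depend on the size of the subset. At Month 6, where marker testing starts, less use could have accrued.

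**4. Size for per-protocol hip fracture, if that analysis is run**

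The planned hip relative risk of 0.65 (Section 3.5.5.4) stands in for the effect of the drug. The placebo hazard is multiplied by `1 − q(1 − 0.65)`:

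- q = 0.005: factor 0.99825; 0.65 / 0.99825 = 0.6511; log shift 0.0018.
- q = 0.02: factor 0.993; 0.65 / 0.993 = 0.6546; log shift 0.0070.

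With 237 events the standard error of the log hazard ratio is about 2/√237 = 0.130. The shift is therefore 0.013 to 0.054 standard errors, and less still with the fewer events of a per-protocol set.

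**The case against.** The strongest reply is that the list is selective on purpose. Appendix 6.7 says the per-protocol rules are a clinical assessment and not a copy of the entry criteria. Four of the 20 entries are absent and none of the absences is explained, so one more gap does not prove a slip. Subcutaneous calcitonin is also listed as bone-active and also missing, and no error is alleged there.

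The selectivity is real, and counting absences settles nothing by itself. But Appendix 6.7 states its test: whether a deviation may affect or confound efficacy. A class barred for any lifetime use because it acts on bone meets that test, and the other main osteoporosis drug classes are listed. Calcitonin is a weaker case because the protocol permits its intranasal form throughout.

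The second reply is that other safeguards shrink the gap. Keeping a woman on blinded tablets while she takes a prohibited drug needs the agreement of the investigator, the sponsor and the patient. Once tablets stop, the compliance and last-dose rules remove her data. Women randomized in error may be discontinued at the sponsor's discretion, and violators are identified blind before the database is frozen. All of this reduces the number affected. It does not close the gap, because discontinuation is discretionary and blinded screening applies the written rules.

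The third reply, that the effect is negligible and rests on assumed inputs, stands. It sets the priority of the point; it does not make the list correct.

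**Conclusion.** The concern holds, as a minor point. Item 8 omits a prohibited bone-active class, no other per-protocol rule covers its use by a woman who stays on her tablets, and the stated purpose of the rules gives no reason for the omission.

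The likely effect is very small: a movement of at most 0.007 in a marker ratio of 0.30 or 0.40, and about 0.05 standard errors in a per-protocol hip hazard ratio. These figures rest on an assumed 0.5–2% of placebo values affected, none on odanacatib, and stand-in drug effects taken from elsewhere in the protocol. The protocol supplies no frequency of use. The FAS fracture and BMD analyses are not affected, and no primary conclusion is expected to change.

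**What to change.** Before unblinding, add RANK ligand inhibitors as an entry in item 8 of Appendix 6.7. Data would then be excluded from the start of the drug onward, as already happens for bisphosphonates, and prior use would count as it does for the other listed drugs. The timing matters because adding a drug class after unblinding would look data-driven.

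The cost is one line of text and the loss of a few data points from the per-protocol set. Adding non-intranasal calcitonin, to match criterion 10(c), is optional tidying.
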